#### Step 6: Home-Based Exercise Program (HBEP)

HBEP will be available to all patients who are able to ambulate with or without an assistive device (cane or walker), regardless of supplemental oxygen use. If the patient expresses interest in HBEP, the CHW will schedule the appointment at a clinical practice at the Mount Sinai Hospital. Patients in the intervention arm of the study will undergo an evaluation at Mount Sinai Hospital for home exercise by a clinician. [name] and [name] will serve as clinicians. [name] is a board-certified internist who practices general internal medicine. [name] is a pulmonologist. Both have done extensive research with the COPD population. If in-person evaluation is not possible, the patient will undergo an evaluation by video call. The video encounter will only occur if the patient has previously demonstrated during the study that they are capable of communicating clearly and visibly by video call. The patient will undergo a standard evaluation by a clinician employed by Mount Sinai Hospital. The evaluation will have two components, assessment of aerobic capacity using the 6-minute walk test (6MWT), and an assessment of muscular strength using elastic resistance bands. Target exercise intensity will be set at 60-80% of the maximum work rate achieved during the 6MWT, a conservative goal intended to achieve benefit while minimizing risk of fatigue and shortness of breath. Based on the patients' performance during the evaluation, the clinician will select an appropriate band for home use for strength training exercises. During the evaluation, the clinician will monitor the patient's oxygen saturation, heart rate, and respiratory rate. If a video evaluation will be conducted, the study team will mail the patient the following materials before the evaluation is performed: color-coded and latex-free resistance bands of varying resistance levels, a digital pulse-oximeter pre-set up with batteries, a digital automated blood pressure monitor, and a digital wristband activity monitor. These items are easy to use and instructions will be provide for their use, including written instructions, and guidance by video call, and by telephone as need. They will be allowed to keep these materials when their participation in the study ends, no matter the duration of their participation.

	Protocol Name:	Comprehensive Home-based Self-management Support for COPD Patients
	Principal Investigator:	[name], MPH
	Primary Contact Name/Contact Info:	[name]; [contact]; [contact]
	Date Revised:	4/16/21
	Study Number:	STUDY-18-01345

The video evaluation will be performed by a clinician and only if the patient is accompanied by an adult who is physically capable of supporting the patient and participating in the evaluation procedures. The clinician will follow the same procedures described above for the in-person evaluation. This includes 1) the 6-minute walk test, and 2) demonstration of ability to perform various maneuvers using the resistance bands. The accompanying adult will measure the patient’s blood oxygen saturation and pulse using the pulse-oximeter and blood pressure prior to the start of physical activity and at the immediate conclusion of the activity, and provide that information to the clinician performing the evaluation. The clinician will use this information to plan a home-exercise regimen for the patient.

Tablets and Internet access will be provided, as needed, to patients in both the intervention and control arms. If patients have a smart phone, tablet, or computer (hereafter termed “electronic device”), a study tablet will not be provided to them.

If the patient does not have Internet access, the study will provide them with an Internet-wifi connection at no cost to them; the cost-free Internet will be available to them for the duration of the study. At the conclusion of the study, the patients will be allowed to keep the tablet device and the study team will provide them with information about low cost Internet plans in their area.

Tablets will be pre-loaded with videos demonstrating proper inhaler technique for COPD inhaled medicines, breathing techniques, and exercises. They will also be set up with video conference capability. Patients will be provided with a telephone number to call if they have difficulty using the device. If they already own or have access to an electronic device, the study team will send them the videos by email or text message.

During the home visit or telehealth visits that follows, the CHW will provide a timer, a fitness tracker bracelet to measure steps, an elastic resistance band, and an exercise diary. They may also provide the patient with a ergo cycle to enable them to conduct the aerobic exercises sitting down if walking is too burdensome or the patient is considered to be at high fall risk. The CHW and patient will consider the space available for exercise, such as a hallway, common space in the building (e.g., lobby, gathering room, etc.), outdoors during favorable weather, and local facilities like senior centers or churches. Once the area for exercise is selected, the CHW will demonstrate or explain the walking and resistance training routines and observe the patient perform them on his/her own. The two will set a schedule for exercising and post the schedule and instructions prominently in the home.

	Protocol Name:	Comprehensive Home-based Self-management Support for COPD Patients
	Principal Investigator:	[name], MPH
	Primary Contact Name/Contact Info:	[name]; [contact]; [contact]
	Date Revised:	4/16/21
	Study Number:	STUDY-18-01345

If the patient is unable to ambulate, or their gait appears unstable, they will be provided with a hand pedal ergometer, which they will use in place of walking for exercise. They will be allowed to keep the ergometer at completion of the study.

Resistance training will consist of a simple routine of upper and lower extremity extension and abduction movements with the elastic band. Each movement will be performed for 8-12 repetitions. The walking routine will last 20-40 minutes and the patient's pace will be guided by an audible click from the timer that is set by the CHW. The patient will be asked to perform the complete exercise routine 5 days a week. The CHW will directly supervise the patient in person or over the phone multiple times over the 6-month intervention period. She will call periodically to support the patient when she is unable to visit.

The clinician will provide supervision of the CHW. This will include reviewing all cases in person or by phone every 7-14 days. Patients will be asked to reduce the intensity of exercise or rest for 5-10 minutes if they develop an uncomfortable level of shortness of breath or fatigue, and to stop exercising if they have symptoms that cause distress or discomfort and do not resolve after rest. Low literacy education methods will be used to ensure their understanding and retention of these instructions. The CHW will maintain communication with the clinician by HIPAA compliant secure email and telephone to report patient performance, trouble shoot problems, and to receive continuing education.

Step 7: Follow-up and Maintenance. The CHW will recommend that meetings occur 1, 4, 8, and 12 weeks after intake and telephone follow-ups weekly through week 8 and monthly thereafter until month 6 when the intervention ends. Calls may be made more often to cognitively impaired patients to enhance information retention. Importantly, the patient and CHW will have the flexibility to tailor the number and frequency of encounters as they see fit. During follow up the CHW will assess patients' progress with SMB, their goals, and their symptoms.

Step 8: Graduation. SaMBA-COPD patients will receive a certificate upon program completion. Description of Procedures Being Performed

a. Patients and Settings. We will recruit patients from the outpatient general medicine and pulmonary practices of Mount Sinai Hospital. Inclusion Criteria: 1) age >40 years; 2) community dwelling; 3) chart-document severe or very severe COPD (FEV1<70% predicted); 4) prescribed any daily medication for COPD; 5) English or Spanish speaking; 6) Smoking history # 10 pack-years; 7) COPD-related ED/hospitalization # 1 visit within the past 12 months. Exclusion Criteria: Diagnosis in the clinical record of dementia, because the study focuses on patients with capacity to independently perform SMB.

	Protocol Name:	Comprehensive Home-based Self-management Support for COPD Patients
	Principal Investigator:	[name], MPH
	Primary Contact Name/Contact Info:	[name]; [contact]; [contact]
	Date Revised:	4/16/21
	Study Number:	STUDY-18-01345

b. Community Health Workers: CHWs are a part of the study team and will be assessed for internal quality assurance purposes only. Currently there is not a clear intent to contribute to generalizable knowledge with this data. If the data are re-examined or re-analyzed and new information surfaces that would contribute to generalizable knowledge, an application will be submitted to the IRB. Their performance is being evaluated for internal quality assurance for this study.

c. Recruitment and Interviewing. We will identify potentially eligible patients through queries of the Epic clinical record. RAs will obtain permission from the physician to recruit their patient then send a letter to the patient describing the study. One week later, the RA will phone the patient to answer questions and check eligibility of the participant. Eligible patients will be scheduled for an in-person baseline interview and enrolled in the study. Baseline interviews will occur at a location/time of the patient's choosing. RAs will reschedule missed interview appointments up to three times, after which patients will be considered dropouts. RAs blinded to treatment allocation will interview patients at 6 and 9 months.

d. Video Conferencing. Some visits with the community health worker may take place over Zoom conferencing or VSee video call, the Icahn School of Medicine approved HIPAA compliant version. Both Zoom and VSee ensure HIPAA compliance by preventing the sharing and collection of PHI and by encrypting audio and video data (for more information: <https://zoom.us/docs/doc/Zoom-hipaa.pdf>; <https://vsee.com/hipaa>).

Enrolled participants will be contacted via phone or email, based on their preferred method of contact, and provided with a link and password to access a Zoom session. A trained member of the research staff will meet with the participant over Zoom at the scheduled time to complete the visit. As an alternative method, participants will be sent a text or email with a link to open up a VSee video call.

If participant responses during the visit raise any concerns about patient safety, the research staff member will follow a modified version of the study protocol for risk assessment. The modification will be as follows:

- Rather than bringing the Principal Investigator or other licensed clinician into the room to meet with the participant in person, the clinician will be contacted via phone and, with the participant's permission, will be given access to join the video conference and conduct an additional assessment via this platform.
- If the clinician determines that that participant is at elevated risk for suicide, the patient is notified by the clinician that 911 will be called and that this will result in an ambulance being sent to their residence to make sure that the subject is okay. The study coordinator remains on the telephone with the patient until the ambulance arrives. The 911 operator is notified if the patient ends the video conferencing call abruptly or hangs up.

	Protocol Name:	Comprehensive Home-based Self-management Support for COPD Patients
	Principal Investigator:	[name], MPH
	Primary Contact Name/Contact Info:	[name]; [contact]; [contact]
	Date Revised:	4/16/21
	Study Number:	STUDY-18-01345

e. Randomization. Randomization will occur immediately after the baseline interview is complete. To obtain the assignment, the RA will access an online program in REDCap that implements the algorithm.

f. Control Arm. The attention control is designed to isolate the impact of screening for self-management barriers, targeted self-management support, and HBEP. The attention control will consist of 3 visits by a CHW to the home to review the COPD education booklet (COPD 1-2-3). During the first visit, this CHW will review the COPD 1-2-3 booklet in its entirety with the patient. During visits 2 and 3, the CHW will make a visit to "check in" with the patient, ask how they are doing with their respiratory symptoms, and review any sections of the COPD 1-2-3 booklet the patient chooses. The CHW will recommend visits every 2 months but the patient and CHW may choose to modify the interval as needed. If the patient appears to be experiencing worsening respiratory symptoms during any visit, the CHW will notify the patient's physician.

g. Quantitative Data Collection. Baseline, 6- and 9-month interviews will be in-person or over the phone in English or Spanish. Bilingual RAs will conduct them at home or in clinical spaces, by patient preference, using laptop computers and REDCap software, as we do with all of our research.

Primary Outcomes: COPD symptoms, inhaler technique, and exercise activity. COPD symptoms will be measured with the 8-item COPD Assessment Test (CAT) (score range 0-40), the 14-item Chronic Respiratory disease Questionnaire (CRQ), and the Medical Research Council Scale. Inhaler technique: We will assess proficiency in use of MDI and DPI placebo devices (Spirit Medical Devices, Murrysville, PA) and medication tracking devices (Propeller Health, Madison Wisconsin) using validated checklists and adapt these checklists for technique assessment with users of Elipta and Respimat inhalers. The Propeller Health devices can aid patients in medication adherence and understanding of their triggers for COPD and asthma. Exercise in the past 7 days will be measured with the 13-item Physical Activity Adult Questionnaire (PAAQ) and a wearable activity monitor, the Actigraph, which will be worn for 1 week intervals at baseline, 6 and 9 months. Secondary Outcomes. Self-reported medication adherence will be measured with the self-reported Medication Adherence Reporting Scale (MARS)., and with an electronic monitoring device that is attached to the inhaler. Exercise tolerance will be measured at baseline, 6- and 9-months using the 6- minute walk test (6MWT). We will ask about use of an action plan for COPD exacerbation.

h. Fidelity. Fidelity will be assessed through abstraction of CHWs' documentation in Community Health Works' documentation, direct observation of the CHWs, and qualitative exit interviews with patients and CHWs. The project manager will conduct unannounced

	Protocol Name:	Comprehensive Home-based Self-management Support for COPD Patients
	Principal Investigator:	[name], MPH
	Primary Contact Name/Contact Info:	[name]; [contact]; [contact]
	Date Revised:	4/16/21
	Study Number:	STUDY-18-01345

observations of each CHW monthly during the trial. She will also audio/video tape these encounters to review with the CHW for skills development.

i. **Qualitative Data Collection and Analysis.** We will conduct semi-structured exit interviews with patients and CHWs to assess feasibility and perceptions of SaMBA-COPD to guide refinement. Interviews will follow the month 9 interview or at study dropout (30-45 minutes; compensation, \$20). Topics will include satisfaction, burden (physical, emotional, social), convenience, perceived positive or negative effects, and appropriateness. At trial completion, we will conduct qualitative interviews with CHWs and their supervisor and PR staff and physicians to assess the same topics. All interviews will be audio/video-recorded. These interviews will be used for internal evaluation and quality improvement.

j **Quantitative Data Analysis.**

Primary analyses. We will analyze outcomes on the intention-to-treat principle. The primary outcomes are CAT score, ICS technique, and PAAQ scores at 9 months.

Description of Data that Will Be Collected Including Long-Term Follow-Up

Disease beliefs: will be measured with the brief Illness Perceptions Questionnaire (IPQ; available in English and Spanish) that includes items for each of the 5 cognitive domains of the SRM.(15) Medications Beliefs: We will use the Beliefs about Medicines Questionnaire, an English and Spanish validated 10-item scale that measures beliefs about controller medication in 2 subdomains: necessity and concerns (reliability: 0.80). (16) Items will be added to assess expectations of benefits and emotional representations about medications (worried about side effects or addiction, upset about medication regimen, etc.).

Adherence: COPD controller medication adherence, electronically measured: Objective measurement using the Smartinhaler electronic device for metered dose inhalers (MDIs) and the Smartdisk for dry powder inhalers (DPIs) for 4 weeks after each research interview. RAs will attach the monitoring device to the inhaler, and patients will return them in a pre-stamped envelope. Adherence will be defined as use of medications on #70% of days prescribed, a commonly applied convention.

Cognitive: Quick mild cognitive impairment screen (QMCI).

Lifestyle: physical activity, electronically measured: objective measurement using Actigraph. Physical activity adult questionnaire (PAAQ). Smoking/alcohol/drug activity. Activities of daily living questionnaire (ADL), general health (single item). Comorbidities (Charlson Index).

Depression/anxiety: Patient health questionnaire 9 (PHQ-9), General anxiety disorder 7 (GAD-7)

	Protocol Name:	Comprehensive Home-based Self-management Support for COPD Patients
	Principal Investigator:	[name], MPH
	Primary Contact Name/Contact Info:	[name]; [contact]; [contact]
	Date Revised:	4/16/21
	Study Number:	STUDY-18-01345

Health services: health service utilization (ED/hospitalizations). We will obtain data on these outcomes by self-report and from the NYS SPARCS data system.

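### A home interview can reveal the arm of an exercise-programme participant to the blinded research assistant, and the plan has no step to protect the blind

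*Protocol*

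**What the plan says.** **What is placed in the home.** Under Step 6 of the protocol, "the CHW will provide a timer, a fitness tracker bracelet to measure steps, an elastic resistance band, and an exercise diary". Of the exercise plan it says: "The two will set a schedule for exercising and post the schedule and instructions prominently in the home". Some patients also receive a cycle or a hand ergometer; of the latter, "They will be allowed to keep the ergometer at completion of the study". Materials mailed ahead of a video evaluation, resistance bands among them, may be kept too.

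**Who receives it.** The exercise programme is part of the intervention and depends on the patient wanting it: "If the patient expresses interest in HBEP, the CHW will schedule the appointment at a clinical practice at the Mount Sinai Hospital". Item f (Control Arm) confirms that it separates the arms: "The attention control is designed to isolate the impact of screening for self-management barriers, targeted self-management support, and HBEP".

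**Who assesses, and where.** Item c (Recruitment and Interviewing) states: "RAs blinded to treatment allocation will interview patients at 6 and 9 months". Item g (Quantitative Data Collection) states: "Baseline, 6- and 9-month interviews will be in-person or over the phone in English or Spanish", and then: "Bilingual RAs will conduct them at home or in clinical spaces, by patient preference".

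**What is assessed.** Item g has inhaler technique judged by checklist while the patient handles placebo devices. Item j (Quantitative Data Analysis) names CAT, inhaler technique and PAAQ at 9 months as the primary outcomes.

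Neither document says that exercise materials are put away before a research visit, that patients are asked not to mention study activities, or that a breach of the blind is recorded.

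**The concern.** Three instructions meet in one room. One puts arm-specific material on display, one allows the assessor into that home, and one describes the assessor as blinded. Each can be followed exactly and the blind can still fail. Separating staff does not help: a research assistant who has never seen the REDCap assignment can still read a schedule on the wall.

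Technique scoring is where this matters most. The checklists are described as validated, but deciding whether a step was done properly remains a judgement, and an assessor who knows the patient was coached may be more lenient. CAT and PAAQ are answered by the patient, who knows what was received. An unblinded interviewer can still affect prompting and clarification, but hiding the schedule does nothing about the patient's own reporting. Actigraph and electronic adherence data should be little affected.

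The SAP's difference-in-differences analysis does not remove the problem. The baseline interview comes before randomization, so any shift enters at follow-up only and passes in full into the estimated effect.

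**Working it through.** **1. Is there a route to unblinding?** Setting the sections side by side:
- Arm-specific cue: the posted schedule and instructions, bands, diary, and an ergometer where issued (Step 6). Controls are not given the exercise programme (item f).
- Access: home interviews are allowed at 6 and 9 months (item g).
- Claimed safeguard: blinded interviewers (item c).
- Protective step: none found in either document.

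The route exists, but only for intervention patients who both take up the programme and are interviewed at home.

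**2. How many are exposed?** The documents give 29 patients per arm and neither of the two shares needed, so exposure lies anywhere from 0 to 29 of 29. Write u for uptake and h for the share interviewed at home with materials still in view; the exposed fraction is u × h, treating the two as independent.

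**3. What shift follows?** The plan has no figure of its own to reproduce. Let b be the rater shift, in SD of the technique score, when the arm is known. Then
- bias in the arm difference: d = u × h × b
- standard error with 29 per arm: √(2/29) = 0.263 SD
- two-sided false-positive rate at nominal 5% with no true effect: Φ(d/0.263 − 1.96) + Φ(−d/0.263 − 1.96)

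The values of u, h and b are all assumptions, with b from 0.2 to 0.5.

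| u | h | Exposed of 29 | d (SD) | d / SE | False-positive rate |
|---|---|---|---|---|---|
| 25% | 25% | 1.8 | 0.013 to 0.031 | 0.05 to 0.12 | 5.0% to 5.2% |
| 50% | 50% | 7.2 | 0.05 to 0.125 | 0.19 to 0.48 | 5.4% to 7.6% |
| 75% | 75% | 16.3 | 0.113 to 0.281 | 0.43 to 1.07 | 7.1% to 18.8% |
| 100% | 100% | 29 | 0.2 to 0.5 | 0.76 to 1.90 | 11.9% to 47.8% |

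For the second row: 0.5 × 0.5 × 0.2 = 0.05 and 0.5 × 0.5 × 0.5 = 0.125; 0.05/0.263 = 0.19 and 0.125/0.263 = 0.48.

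The standard error is for a comparison at one time point. For change from baseline it is multiplied by √(2(1 − ρ)), where ρ is the baseline–follow-up correlation; that factor is 1 at ρ = 0.5. The documents give no ρ.

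**The case against.** The strongest reply is that the plan does not send assessors into intervention homes as a rule. Interviews may be by phone or in clinical space, Section 1 places research activities in the Center for Advanced Medicine, and the exercise programme is taken up only by those who want it. This stands, and it makes the concern conditional. The phone option helps least for technique, however, since the protocol describes no way to observe device handling by phone.

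The second reply is timing. The intervention ends at month 6 and the primary time point is month 9. A reader might infer that the primary assessment is unblinded; the documents do not support that, because they do not say whether the schedule is still posted. Nor do they say that it is taken down, and retained bands or an ergometer can still be in view.

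Third, some cues are weak. Both arms wear an Actigraph for a week at each assessment, so a wearable alone does not mark the arm. Tablets holding exercise videos may go to either arm. The schedule, diary and bands remain specific to the programme.

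Fourth, checklists limit judgement, the text does not name the technique scorer, and the SAP says the trial was not powered to detect differences between arms. These points reduce the consequence without removing it: the SAP still applies P < 0.05 to all outcomes, and a feasibility trial ought to test whether its blinding works.

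**Conclusion.** The gap is real, and it is narrow. Followed as written, the plan can defeat its own blinding when an HBEP participant is interviewed at home, and the main exposure is inhaler technique. This assumes that the interviewing research assistant scores technique, which the protocol implies but does not state.

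At 50% uptake and 50% home interviews, about 7 of 29 intervention patients are exposed and the bias is 0.05 to 0.125 SD, roughly 0.2 to 0.5 of a standard error. Both shares and the rater shift are assumed, and any removal of materials by month 9 would lower the figure.

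Two stronger readings should be resisted. A reader might infer that the arm is visible at every follow-up visit; phone and clinic interviews and optional uptake rule out assuming that. A reader might also infer that CAT and PAAQ are compromised to the same degree; for those, only the interviewer's influence is in question.

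**What to change.** Add to items c and g of the procedures section:

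1. The appointment call before each 6- and 9-month interview uses one script in both arms. It asks patients to put away all study materials other than the Actigraph and inhaler monitor, and not to mention study visits or activities.
2. The research assistant scores inhaler technique before asking the other questions.
3. The research assistant records the interview location, whether arm-revealing materials were seen, and the guessed arm.

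Report these three items by arm and word the blinding claim to match. Keep all visits in the intention-to-treat analysis. Dropping visits marked unblinded would remove mainly intervention patients who took up the exercise programme, which is selection after randomization in one arm. Keep the patient's choice of location: a clinic default could add missed interviews, and item c already counts patients as dropouts once three reschedulings are used up.

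The cost is a script line, an ordering rule and a few REDCap fields. The SAP is dated September 2021 and written in the past tense. If follow-up is already complete, what remains is to report interview location where it was recorded and to qualify the statement that assessors were blinded.

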Research Recruitment and Study Arm Assignment: We will identify potentially eligible patients and will obtain permission from the physician to recruit their patient. We will send a letter to the patient describing the study. One week later, the RA will phone the patient to answer questions and check eligibility of the participant. Eligible patients will be scheduled for an in-person or phone baseline interview, consented and enrolled in the study. We will assess the participant's inhaler technique, electronic medication adherence, and physical activity through a wearable activity monitor. The data from the electronic medication adherence device is for research purposes only. There are no studies demonstrating that providing such data to patients or their doctors improves their medication adherence, thus providing these data to them is unwarranted. The participant will then be randomized to the intervention or control arm.

B.3) SaMBA-COPD Intervention.

	Protocol Name:	Comprehensive Home-based Self-management Support for COPD Patients
	Principal Investigator:	[name], MPH
	Primary Contact Name/Contact Info:	[name]; [contact]; [contact]
	Date Revised:	4/16/21
	Study Number:	STUDY-18-01345

Step 1: Outreach and Engagement. The project manager will notify the CHW supervisor when an eligible and consented patient is randomized to receive care the intervention and will provide the patient's name and contact information (see Description of Procedures Being Performed for recruitment and randomization). The CHW will call the patient within 7 days of consent to schedule a home visit. The CHW will encourage caregivers to join all meetings.

Step 2: Intake. The CHW will perform an intake interview that includes collection of basic information about the patient and their health and healthcare, including medications, intended to enable them to understand their health problems and provide them with chronic illness self-management support.

Step 3: Symptom assessment, medication adherence, and inhaler technique. The CHW will assess the patients' symptoms, adherence to medications, and check inhaler technique following a standardized protocol, and correct errors in inhaler use if identified.

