## 8. Payments/Reimbursements to Subjects:

If participants agree to take part in this research study, they will be paid for time and effort to participate in the research interviews. They will not be paid for intervention or control activities, and thus will not be paid for visits with the community health worker, pharmacist, or clinician, or visits with the research coordinator to review the COPD educational booklet.

For research interviews, a participant may receive up to \$255 for participating in this study. A participant will be paid \$65 after the completion of the each interview. If all 3 interviews are completed, participants will be paid a total of \$195. Up to an additional \$20 will be given to subjects after every interview once they return the electronic monitoring device for the medication (\$10) and an accelerometer (\$10). Participants will be paid in cash or money order at the completion of each interview. Payments will be for the research interviews only.

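### The attention control does not match CHW contact, so the trial can estimate package versus package but cannot isolate the named components; the protocol also disagrees on who makes the control visits

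*Protocol*

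**What the plan says.** Protocol section 3(e), paragraph f (Control Arm), gives the comparator its purpose: "The attention control is designed to isolate the impact of screening for self-management barriers, targeted self-management support, and HBEP". It then describes the content: "The attention control will consist of 3 visits by a CHW to the home to review the COPD education booklet (COPD 1-2-3"). The first visit covers the whole booklet. At the second and third, the CHW is to "ask how they are doing with their respiratory symptoms, and review any sections of the COPD 1-2-3 booklet the patient chooses". Visits are recommended every two months and the interval may be changed.

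For the intervention arm, Step 2 of section 3(e) begins contact with an intake: "The CHW will perform an intake interview that includes collection of basic information about the patient". Step 7 then recommends "meetings occur 1, 4, 8, and 12 weeks after intake and telephone follow-ups weekly through week 8 and monthly thereafter until month 6", which closes the intervention period. Step 7 also says that "the patient and CHW will have the flexibility to tailor the number and frequency of encounters as they see fit", and that at follow-up the CHW assesses "progress with SMB, their goals, and their symptoms". Steps 5 and 6 add voluntary pharmacist counselling about a rescue pack, a clinician evaluation for the home-based exercise programme (HBEP), and CHW supervision of exercise an unstated number of times.

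On who makes the control visits, section 8 (Payments/Reimbursements) says participants are not paid for intervention or control activities, and lists these as "visits with the community health worker, pharmacist, or clinician, or visits with the research coordinator to review the COPD educational booklet".

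The SAP specifies a single difference-in-differences approach comparing the two arms. It names no component analysis and no term for amount of contact, and it describes the study as an unpowered feasibility trial.

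**The concern.** An attention control supports a claim about content only if the attention itself is roughly equal between arms. If one arm is telephoned weekly for two months and the other is visited three times in six, a difference could come from the barrier screening, the tailored support, the exercise programme, or simply from more frequent contact. Two of the three primary outcomes in section 3(e), paragraph j (CAT and PAAQ), are patient-completed questionnaires, and patients know how often they are contacted. A null result would be equally hard to attribute.

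What is at stake is the wording of the conclusion. A report that repeats the control-arm sentence would credit a difference, or its absence, to three named components when the design cannot do so.

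The second issue is a contradiction about the delivery of a trial arm. If the research coordinator reviews the booklet with controls, the arms differ by deliverer as well as by content and amount of contact. Section 12 has coordinators trained in survey administration, and section 3(e), paragraph c, requires blinded staff for the 6- and 9-month interviews, so the two roles would have to be kept apart.

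**Working it through.** The check is a direct count from the recommended schedules.

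**Control arm.** A 6-month control period (section 3(d), Study Duration) with a visit every 2 months gives 6 / 2 = 3, which reproduces the 3 visits in paragraph f. No calls are scheduled.

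**Intervention arm.** The documents state no total. Inputs are from Steps 2 and 7.

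- Meetings: intake (1) + weeks 1, 4, 8 and 12 (4) = 5.
- Weekly calls: 8 if a call is made every week from 1 to 8; 5 if the meetings in weeks 1, 4 and 8 replace that week's call (leaving weeks 2, 3, 5, 6 and 7).
- Monthly calls: 4 if months 3 to 6 all count; 2 if the week-12 meeting stands for month 3 and month 6 is only the end point (leaving months 4 and 5).
- Calls in total: 5 + 2 = 7 at the lowest, 8 + 4 = 12 at the highest.

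| | Intervention | Control | Gap | Ratio |
|---|---|---|---|---|
| Meetings, including intake | 5 | 3 | 2 | 5/3 = 1.7 |
| Scheduled calls | 7 to 12 | 0 | 7 to 12 | – |
| All CHW encounters | 12 to 17 | 3 | 9 to 14 | 12/3 = 4.0 to 17/3 = 5.7 |
| All, intake not counted | 11 to 16 | 3 | 8 to 13 | 11/3 = 3.7 to 16/3 = 5.3 |

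Every combination of these conventions gives at least 11 against 3. Most of the gap is telephone contact; face to face it is 5 against 3.

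**Not in the count, and described only for the intervention arm:** the clinician exercise evaluation and CHW exercise supervision (Step 6), and the pharmacist contacts (Step 5). For setting up the rescue pack, Step 5 describes at most 2 pharmacist contacts: one visit and one follow-up at 7 to 10 days. Both depend on physician and patient agreement.

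**What the analysis can identify.** With two arms there is one between-arm contrast per outcome and time point. Content and contact change together between the arms, so that contrast measures their joint effect.

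**Who makes the control visits.** Paragraph f assigns the booklet visits to a CHW. Section 8 names CHW visits and then, as a separate item, booklet visits with the research coordinator. Both passages cannot describe the same delivery of the control.

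**The case against.** The strongest reply is that nothing in the analysis depends on the sentence. The plan is intention-to-treat, the SAP compares intervention with control, and neither document states a component hypothesis. The sentence can also be read jointly, as the three elements together over and above booklet education and home visits. On that reading much of the extra contact is the means by which support is delivered: Step 7 uses follow-up to review progress and goals, Step 5 allows more frequent encounters when memory is impaired, and Step 6 uses visits and calls to supervise exercise.

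Most of this stands, and it is why the point is minor. It does not rescue the sentence. Even read jointly, contact is unmatched, and the documents give no basis for dividing it into delivery of content and general attention.

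The counts also have limits. They are recommended and not delivered, the calls are of unstated length, and Step 7 lets the number vary. The figure of 12 to 17 against 3 should not be read as a ratio of face-to-face time.

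Two stronger readings are tempting and not supported. A reader might infer that rescue-pack counselling is a component left out of the control-arm sentence. It sits under Step 5, on addressing identified barriers, so it falls naturally within targeted support. A reader might also infer that unblinded coordinators will collect outcomes. The documents do not say that the roles overlap, and the blinding requirement in paragraph c already implies that whoever delivers control visits cannot do those interviews.

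**Conclusion.** The control does not have the isolating property the protocol gives it. Recommended CHW contact is 12 to 17 encounters against 3 (11 to 16 if intake is left out), made up of 5 against 3 meetings and 7 to 12 calls against none, with further clinician, exercise-supervision and pharmacist contact in the intervention arm only. This assumes the recommended schedules are followed; actual contact could be lower or higher.

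It would be wrong to conclude that the randomised comparison is biased or that the analysis must change. The comparison is valid for the effect of the whole intervention package against the control package. No claim is made about effect size, power or error rate.

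The conflict between paragraph f and section 8 is real, and the documents do not settle it. Severity is minor for both parts.

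**What to change.** 1. Replace the sentence on isolation in section 3(e), paragraph f, with: *The trial estimates the effect of the whole SaMBA-COPD package, including its additional CHW, clinician and pharmacist contact, versus the control package; it does not separate content from contact.*
2. Reconcile paragraph f with section 8 on who makes the control booklet visits. If research coordinators make them, apply the blinding requirement of paragraph c so that the same people do not conduct the 6- and 9-month interviews.
3. Optionally, report delivered contacts by type and arm from existing records.

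Item 1 is wording only and changes nothing that either arm receives; its price is a narrower causal claim. Item 2 is wording too, plus keeping the two roles separate if coordinators prove to make the visits. Item 3 needs some descriptive work. Paragraph h (Fidelity) provides for abstraction of CHW documentation but does not say that contact counts are taken or that both arms are covered, and pharmacist and clinician contacts may sit in other records. Paragraph b restricts assessment of CHWs to internal quality assurance. Whether that covers patient contact counts is unclear and should be settled first.
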